4 CONTENTS

The analyses will be performed on the Analysis set specified for each table.

Missing data will not be imputed and so patients with missing data will be excluded from the analyses of that variable(s).

If the investigator is unable to collect the requested information the data will be “NK” (Not Known) or “NA” (Not Available), if the investigator did not record the information the data will be “Not Recorded”.

The UPSWING study has descriptive objectives and no specific comparison will be performed. The estimation of confidence intervals limits will be performed, where relevant.

4.1 UNCOMMON MUTATION COHORT

4.1.1 Patient disposition, analysis sets and criteria violations

Table 1-UNC. Patient disposition (ENROLLED PATIENTS of the Uncommon Mutation Cohort)

For each center, the table will provide absolute and relative frequencies of:

- patients ENROLLED in the UPSWING study (as defined in Chapter 2.3) in the cohort
- patients ELIGIBLE for the UPSWING study (as defined in Chapter 2.3) in the cohort

Percentages will be calculated by column; percentages will be calculated by row only for "Overall in the cohort".

Figure 1-UNC. Workflow of analysis sets and reasons for violations (ENROLLED PATIENTS of the Uncommon Mutation Cohort)

A figure with the workflow of analysis sets and reasons for violations will be provided; the hierarchy of violated criteria specific for the cohort (as defined in Section 2.5) will be applied, so that each violator will be classified with only one major violation (even in case of multiple violations).

Table 2-UNC. Reasons for violations (ENROLLED PATIENTS of the Uncommon Mutation Cohort)

The table will describe the reasons for patient non-eligibility and non-evaluability (considering each criterion listed in Section 2.3).

Absolute and relative frequency distribution will be provided.

For each evaluability criterion, percentages will be computed out of the total number of enrolled patients in the cohort.

Table 3-UNC. Duration of observation (ELIGIBLE PATIENTS of the Uncommon Mutation Cohort)

The table will provide main descriptive statistics (mean, standard deviation, quartiles, min, max) of duration of observation window (in months) starting from the first-line treatment start (see "Computed variables" chapter)

Descriptives will be calculated over the number of ELIGIBLE PATIENTS in the cohort.

4.1.2 Demographic and clinical characteristics

Table 4-UNC. Socio-demographics (ELIGIBLE PATIENTS of the Uncommon Mutation Cohort)

The table will provide:

- descriptive statistics (mean, standard deviation, quartiles, min, max) of “Age at start of first-line treatment” [[PI. PI_age](#)];
- patients’ distribution (absolute and relative frequency) by “Gender” [[PI. PI_gender](#)];
- patients’ distribution (absolute and relative frequency) by “Ethnicity” [[PI. PI_ethn](#), [PI.ethn_sp](#)], including also those cases when ethnicity was not provided (according to the field [[PI. PI_cons_ethn_YN](#)] = “No”).

Descriptives and percentages will be calculated over the number of ELIGIBLE PATIENTS in the cohort.

Table 5-UNC. Physical examination and smoking habits at start of first-line treatment (ELIGIBLE PATIENTS of the Uncommon Mutation Cohort)

The table will provide:

- patients’ distribution (absolute and relative frequency) by classes of BMI at start of first-line treatment (see “Computed variables” chapter)
- patients’ distribution (absolute and relative frequency) by “Smoking status” [[SM. SM_status](#)];
- descriptive statistics (mean, standard deviation, quartiles, min, max) of “Estimated amount of cigarettes consumed on average each day” [[SM. SM_cig_num](#)];
- descriptive statistics (mean, standard deviation, quartiles, min, max) of smoking duration (years) at start of first-line treatment (see “Computed variables” chapter)

Descriptives and percentages will be calculated over the number of ELIGIBLE PATIENTS in the cohort.

Table 6-UNC. Clinical characteristics (ELIGIBLE PATIENTS of the Uncommon Mutation Cohort)

The table will provide:

- patients’ distribution (absolute and relative frequency) by “Patient’s ECOG Performance Status” at start of first-line treatment [[First-line treatment period / CCPE. CCPE_ECOG](#)]
- patients’ distribution (absolute and relative frequency) by “Patient’s ECOG Performance Status” at start of second-line treatment [[Second-line treatment period / CCPE. CCPE_ECOG](#)], considering only patients with Number of NSCLC treatment lines >1 (see “Computed variables” chapter)
- patients’ distribution (absolute and relative frequency) by changes in ECOG PS at start of second-line treatment with respect to start of first-line treatment (see “Computed variables” chapter), considering only patients with Number of NSCLC treatment lines >1 (see “Computed variables” chapter).

Descriptives and percentages will be calculated over the number of ELIGIBLE PATIENTS in the cohort, unless differently specified.

Table 7-UNC. NSCLC features (ELIGIBLE PATIENTS of the Uncommon Mutation Cohort)

The table will provide:

- patients’ distribution (absolute and relative frequency) by “Tumor histology” at NSCLC diagnosis [[DIAG. DIAG_hist](#), [DIAG_hist_sp](#)]
- patients’ distribution (absolute and relative frequency) by NSCLC stage at start of first-line treatment (see “Computed variables” chapter)
- descriptive statistics (mean, standard deviation, quartiles, min, max) of Duration of NSCLC until start of first-line treatment (in months) (see “Computed variables” chapter)
- descriptive statistics (mean, standard deviation, quartiles, min, max) of Duration of NSCLC until start of index EGFR-TKI therapy (in months) (see “Computed variables” chapter)

Descriptives and percentages will be calculated over the number of ELIGIBLE PATIENTS in the cohort.

4.1.3 Mutational Status

Mutational Status	
Number of NSCLC treatment lines	1
Number of NSCLC treatment lines	2
Number of NSCLC treatment lines	3
Number of NSCLC treatment lines	4
Number of NSCLC treatment lines	5
Number of NSCLC treatment lines	6
Number of NSCLC treatment lines	7
Number of NSCLC treatment lines	8
Number of NSCLC treatment lines	9
Number of NSCLC treatment lines	10
Number of NSCLC treatment lines	11
Number of NSCLC treatment lines	12
Number of NSCLC treatment lines	13
Number of NSCLC treatment lines	14
Number of NSCLC treatment lines	15
Number of NSCLC treatment lines	16
Number of NSCLC treatment lines	17
Number of NSCLC treatment lines	18
Number of NSCLC treatment lines	19
Number of NSCLC treatment lines	20
Number of NSCLC treatment lines	21
Number of NSCLC treatment lines	22
Number of NSCLC treatment lines	23
Number of NSCLC treatment lines	24
Number of NSCLC treatment lines	25
Number of NSCLC treatment lines	26
Number of NSCLC treatment lines	27
Number of NSCLC treatment lines	28
Number of NSCLC treatment lines	29
Number of NSCLC treatment lines	30
Number of NSCLC treatment lines	31
Number of NSCLC treatment lines	32
Number of NSCLC treatment lines	33
Number of NSCLC treatment lines	34
Number of NSCLC treatment lines	35
Number of NSCLC treatment lines	36
Number of NSCLC treatment lines	37
Number of NSCLC treatment lines	38
Number of NSCLC treatment lines	39
Number of NSCLC treatment lines	40
Number of NSCLC treatment lines	41
Number of NSCLC treatment lines	42
Number of NSCLC treatment lines	43
Number of NSCLC treatment lines	44
Number of NSCLC treatment lines	45
Number of NSCLC treatment lines	46
Number of NSCLC treatment lines	47
Number of NSCLC treatment lines	48
Number of NSCLC treatment lines	49
Number of NSCLC treatment lines	50
Number of NSCLC treatment lines	51
Number of NSCLC treatment lines	52
Number of NSCLC treatment lines	53
Number of NSCLC treatment lines	54
Number of NSCLC treatment lines	55
Number of NSCLC treatment lines	56
Number of NSCLC treatment lines	57
Number of NSCLC treatment lines	58
Number of NSCLC treatment lines	59
Number of NSCLC treatment lines	60
Number of NSCLC treatment lines	61
Number of NSCLC treatment lines	62
Number of NSCLC treatment lines	63
Number of NSCLC treatment lines	64
Number of NSCLC treatment lines	65
Number of NSCLC treatment lines	66
Number of NSCLC treatment lines	67
Number of NSCLC treatment lines	68
Number of NSCLC treatment lines	69
Number of NSCLC treatment lines	70
Number of NSCLC treatment lines	71
Number of NSCLC treatment lines	72
Number of NSCLC treatment lines	73
Number of NSCLC treatment lines	74
Number of NSCLC treatment lines	75
Number of NSCLC treatment lines	76
Number of NSCLC treatment lines	77
Number of NSCLC treatment lines	78
Number of NSCLC treatment lines	79
Number of NSCLC treatment lines	80
Number of NSCLC treatment lines	81
Number of NSCLC treatment lines	82
Number of NSCLC treatment lines	83
Number of NSCLC treatment lines	84
Number of NSCLC treatment lines	85
Number of NSCLC treatment lines	86
Number of NSCLC treatment lines	87
Number of NSCLC treatment lines	88
Number of NSCLC treatment lines	89
Number of NSCLC treatment lines	90
Number of NSCLC treatment lines	91
Number of NSCLC treatment lines	92
Number of NSCLC treatment lines	93
Number of NSCLC treatment lines	94
Number of NSCLC treatment lines	95
Number of NSCLC treatment lines	96
Number of NSCLC treatment lines	97
Number of NSCLC treatment lines	98
Number of NSCLC treatment lines	99
Number of NSCLC treatment lines	100

Table 10-UNC. Approaches for detection of mutations at first-line treatment start (ELIGIBLE PATIENTS of the Uncommon Mutation Cohort) – Secondary objective #3

The table will provide:

- absolute and relative frequency of patients by “Biologic sample(s) used for mutation testing” (according to the fields [*First-line treatment period / MUT1. MUT1_biol_samp, MUT1_biol_samp_sp*]);
- absolute and relative frequency of “Methodology used for mutation testing”, with details of ARMS, sequencing, NGS (according to the fields [*First-line treatment period / MUT1. MUT1_meth, MUT1_meth_sp, MUT1_meth_ARMS, MUT1_meth_ARMS_sp, MUT1_meth_seq, MUT1_meth_seq_sp, MUT1_meth_NGS, MUT1_meth_NGS_sp*])

Descriptives and percentages will be calculated over the number of ELIGIBLE PATIENTS in the cohort.

Approaches for detection of mutations at first-line treatment start (ELIGIBLE PATIENTS of the Uncommon Mutation Cohort)	
Number of NSCLC treatment lines	1
Number of NSCLC treatment lines	2
Number of NSCLC treatment lines	3
Number of NSCLC treatment lines	4
Number of NSCLC treatment lines	5
Number of NSCLC treatment lines	6
Number of NSCLC treatment lines	7
Number of NSCLC treatment lines	8
Number of NSCLC treatment lines	9
Number of NSCLC treatment lines	10
Number of NSCLC treatment lines	11
Number of NSCLC treatment lines	12
Number of NSCLC treatment lines	13
Number of NSCLC treatment lines	14
Number of NSCLC treatment lines	15
Number of NSCLC treatment lines	16
Number of NSCLC treatment lines	17
Number of NSCLC treatment lines	18
Number of NSCLC treatment lines	19
Number of NSCLC treatment lines	20
Number of NSCLC treatment lines	21
Number of NSCLC treatment lines	22
Number of NSCLC treatment lines	23
Number of NSCLC treatment lines	24
Number of NSCLC treatment lines	25
Number of NSCLC treatment lines	26
Number of NSCLC treatment lines	27
Number of NSCLC treatment lines	28
Number of NSCLC treatment lines	29
Number of NSCLC treatment lines	30
Number of NSCLC treatment lines	31
Number of NSCLC treatment lines	32
Number of NSCLC treatment lines	33
Number of NSCLC treatment lines	34
Number of NSCLC treatment lines	35
Number of NSCLC treatment lines	36
Number of NSCLC treatment lines	37
Number of NSCLC treatment lines	38
Number of NSCLC treatment lines	39
Number of NSCLC treatment lines	40
Number of NSCLC treatment lines	41
Number of NSCLC treatment lines	42
Number of NSCLC treatment lines	43
Number of NSCLC treatment lines	44
Number of NSCLC treatment lines	45
Number of NSCLC treatment lines	46
Number of NSCLC treatment lines	47
Number of NSCLC treatment lines	48
Number of NSCLC treatment lines	49
Number of NSCLC treatment lines	50
Number of NSCLC treatment lines	51
Number of NSCLC treatment lines	52
Number of NSCLC treatment lines	53
Number of NSCLC treatment lines	54
Number of NSCLC treatment lines	55
Number of NSCLC treatment lines	56
Number of NSCLC treatment lines	57
Number of NSCLC treatment lines	58
Number of NSCLC treatment lines	59
Number of NSCLC treatment lines	60
Number of NSCLC treatment lines	61
Number of NSCLC treatment lines	62
Number of NSCLC treatment lines	63
Number of NSCLC treatment lines	64
Number of NSCLC treatment lines	65
Number of NSCLC treatment lines	66
Number of NSCLC treatment lines	67
Number of NSCLC treatment lines	68
Number of NSCLC treatment lines	69
Number of NSCLC treatment lines	70
Number of NSCLC treatment lines	71
Number of NSCLC treatment lines	72
Number of NSCLC treatment lines	73
Number of NSCLC treatment lines	74
Number of NSCLC treatment lines	75
Number of NSCLC treatment lines	76
Number of NSCLC treatment lines	77
Number of NSCLC treatment lines	78
Number of NSCLC treatment lines	79
Number of NSCLC treatment lines	80
Number of NSCLC treatment lines	81
Number of NSCLC treatment lines	82
Number of NSCLC treatment lines	83
Number of NSCLC treatment lines	84
Number of NSCLC treatment lines	85
Number of NSCLC treatment lines	86
Number of NSCLC treatment lines	87
Number of NSCLC treatment lines	88
Number of NSCLC treatment lines	89
Number of NSCLC treatment lines	90
Number of NSCLC treatment lines	91
Number of NSCLC treatment lines	92
Number of NSCLC treatment lines	93
Number of NSCLC treatment lines	94
Number of NSCLC treatment lines	95
Number of NSCLC treatment lines	96
Number of NSCLC treatment lines	97
Number of NSCLC treatment lines	98
Number of NSCLC treatment lines	99
Number of NSCLC treatment lines	100

Table 12-UNC. Mutations at second-line treatment start (ELIGIBLE PATIENTS of the Uncommon Mutation Cohort)

The table will provide:

- absolute and relative frequency of patients according to EGFR mutational status at second-line treatment start (see “Computed variables” chapter);
- absolute and relative frequency of patients according to Classification of EGFR uncommon mutations at second-line treatment start (see “Computed variables” chapter);
- absolute and relative frequency of patients according to acquired EGFR mutations at second-line treatment start (see “Computed variables” chapter);
- absolute and relative frequency of patients according to presence/absence of other new mutated genes and detail of new mutations at second-line treatment start (according to the fields [*Second-line treatment period / MUT2. MUT2_oth_gene_start_YN (*)*, *MUT2_oth_gene_start, MUT2_oth_gene_start_sp*]).

(*) in case [*MUT2_oth_gene_start_YN*] = “No”, then the patient’s mutational status for other genes at second-line treatment start will be imputed as the same patient’s mutational status for other genes at first-line treatment.

Descriptives and percentages will be calculated over the number of ELIGIBLE PATIENTS in the cohort, considering only patients with Number of NSCLC treatment lines >1 (see “Computed variables” chapter).

Table 13-UNC. Approaches for detection of mutations at second-line treatment start (ELIGIBLE PATIENTS of the Uncommon Mutation Cohort) – Secondary objective #3

The table will provide:

- absolute and relative frequency of patients by “Biologic sample(s) used for mutation testing” (according to the fields [*Second-line treatment period / MUT2. MUT2_biol_samp, MUT2_biol_samp_sp*]);
- absolute and relative frequency of “Methodology used for mutation testing”, with details of ARMS, sequencing, NGS (according to the fields [*Second-line treatment period / MUT2. MUT2_meth_start, MUT2_meth_start_sp, MUT2_meth_ARMS, MUT2_meth_ARMS_sp, MUT2_meth_seq, MUT2_meth_seq_sp, MUT2_meth_NGS, MUT2_meth_NGS_sp*])

Descriptives and percentages will be calculated over the number of ELIGIBLE PATIENTS in the cohort, considering only patients with Number of NSCLC treatment lines >1 (see “Computed variables” chapter) with “Was mutational status re-evaluated at start of second-line treatment” [*Second-line treatment period / MUT2. MUT2_reeval*] = “Yes”.

[figure not shown]

Table 15-UNC. Mutations at second-line treatment stop/end of observation (ELIGIBLE PATIENTS of the Uncommon Mutation Cohort)

The table will provide:

- absolute and relative frequency of patients according to EGFR mutational status at second-line treatment stop/end of observation (see “Computed variables” chapter);
- absolute and relative frequency of patients according to Classification of EGFR uncommon mutations at second-line treatment stop/end of observation (see “Computed variables” chapter);
- absolute and relative frequency of patients according to acquired EGFR mutations at second-line treatment stop/end of observation (see “Computed variables” chapter);
- absolute and relative frequency of patients according presence/absence of other mutated genes and detail of mutations at second-line treatment stop/end of observation (according to the fields [*Second-line treatment period / MUT2. MUT2_oth_gene_stop_YN* (*), *MUT2_oth_gene_stop, MUT2_oth_gene_stop_sp*]).

(*) in case [*MUT2_oth_gene_stop_YN*] = “No”, then the patient’s mutational status for other genes at second-line treatment stop/end of observation will be imputed as the same patient’s mutational status for other genes at second-line treatment start.

Descriptives and percentages will be calculated over the number of ELIGIBLE PATIENTS in the cohort, considering only patients with Number of NSCLC treatment lines >1 (see “Computed variables” chapter) with “Was mutational status re-evaluated at stop of second-line treatment [...]” [*Second-line treatment period / MUT2. MUT2_reeval_stop*] = “Yes”.

Table 16-UNC. Approaches for detection of mutations at second-line treatment stop/end of observation (ELIGIBLE PATIENTS of the Uncommon Mutation Cohort) – Secondary objective #3

The table will provide:

- absolute and relative frequency of patients by “Biologic sample(s) used for mutation testing” (according to the fields [*Second-line treatment period / MUT2. MUT2_biol_samp_stop, MUT2_biol_samp_stop_sp*]);
- absolute and relative frequency of “Methodology used for mutation testing”, with details of ARMS, sequencing, NGS (according to the fields [*Second-line treatment period / MUT2. MUT2_meth_stop, MUT2_meth_stop_sp, MUT2_meth_ARMS_stop, MUT2_meth_ARMS_stop_sp, MUT2_meth_seq_stop, MUT2_meth_seq_stop_SP, MUT2_meth_NGS_stop, MUT2_meth_NGS_stop_SP*])

Descriptives and percentages will be calculated over the number of ELIGIBLE PATIENTS in the cohort, considering only patients with Number of NSCLC treatment lines >1 (see “Computed variables” chapter) with “Was mutational status re-evaluated at stop of second-line treatment (or within end of observation [...]?)” [*Second-line treatment period / MUT2. MUT2_reeval_stop*] = “Yes”.

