9.7 DATA ANALYSIS

The two cohorts will be analysed separately

- Uncommon mutations
- Sequencing of osimertinib after afatinib

The primary endpoint for both cohorts is time on treatment. Kaplan-Meier estimates will be calculated. In addition, the median will be tabulated along with the two-sided 95% confidence interval, using Greenwood's variance estimate.

The following additional endpoints will be analyzed similarly to the primary endpoint.

- overall survival
- time on treatment until failure of second-line (uncommon cohort only)

Patients who were not known to have discontinued treatment will be censored on the date they were last verified to have been on treatment.

A second round of data collection for additional follow-up may be performed in case a substantial proportion of patients had not discontinued treatment before the estimated median time on treatment at the time of the primary data collection.

Best overall response will be tabulated, as will the following:

- demographics
- disease characteristics
- methodology and material used for mutation classification
- anti-cancer drugs used prior to, or after EGFR-TKI (uncommon cohort only).

These endpoints will be analyzed descriptively.

Within the sequencing cohort, the proportion of patients with different types of resistance mutations observed at the time of discontinuation of osimertinib will be categorized and tabulated.

In this study, data will be gathered retrospectively from patients treated within the conditions of the approved marketing authorization of afatinib. Drug exposure during pregnancy, ADRs with causality to Gilotrif (serious or non-serious) and all fatal AEs will be reported to PV on the NIS AE form - excluding deaths to PD of the underlying malignancy. Safety data will be reviewed and analysed as part routine global pharmacovigilance procedures. All adverse events/reactions collected for the study per protocol will be summarised in the final study report.

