T790M-positive ELIGIBLE PATIENTS (N=xxx)	
Methodology used for mutation testing	
Amplification Refractory Mutation System (ARMS)	xxx (xx.x%)
ddPCR	xxx (xx.x%)
BEAMing	xxx (xx.x%)
...	...
Exon 20 insertion-positive ELIGIBLE PATIENTS (N=xxx)	
Methodology used for mutation testing	
Amplification Refractory Mutation System (ARMS)	xxx (xx.x%)
ddPCR	xxx (xx.x%)
BEAMing	xxx (xx.x%)
...	...
ELIGIBLE PATIENTS with Major uncommon mutations (N=xxx)	
Methodology used for mutation testing	
Amplification Refractory Mutation System (ARMS)	xxx (xx.x%)
ddPCR	xxx (xx.x%)
BEAMing	xxx (xx.x%)
...	...
Other (not included in the previous groups) ELIGIBLE PATIENTS (N=xxx)	
Methodology used for mutation testing	
Amplification Refractory Mutation System (ARMS)	xxx (xx.x%)
ddPCR	xxx (xx.x%)
BEAMing	xxx (xx.x%)
...	...

ELIGIBLE PATIENTS with Compound mutations (N=xxx)	
Methodology used for mutation testing	
Amplification Refractory Mutation System (ARMS)	xxx (xx.x%)
ddPCR	xxx (xx.x%)
BEAMing	xxx (xx.x%)
...	...

Table 12-UNC. Mutations at second-line treatment start (ELIGIBLE PATIENTS of the Uncommon Mutation Cohort)

ELIGIBLE PATIENTS with >1 NSCLC line (N=xxx)		
EGFR mutational status at second-line treatment start	Del19	xxx (xx.x%)
	L858R	xxx (xx.x%)
	L858X (with X being unequal to R)	xxx (xx.x%)
	T790M de novo	xxx (xx.x%)
	G719X	xxx (xx.x%)
	L861Q	xxx (xx.x%)
	S768I	xxx (xx.x%)
	E709X	xxx (xx.x%)
	L747P/S	xxx (xx.x%)
	Q787Q	xxx (xx.x%)
	Exon 20 insertion (*)	xxx (xx.x%)
	Other EGFR mutation(s) (*)	xxx (xx.x%)
	Unknown EGFR mutational status	xxx (xx.x%)
Classification of EGFR uncommon mutations at second-line treatment start	T790M-positive	xxx (xx.x%)
	Exon 20 insertion-positive	xxx (xx.x%)
	Major uncommon mutations	xxx (xx.x%)
	Others	xxx (xx.x%)
	Compound mutations	xxx (xx.x%)

(*) listing might be provided depending on the number of cases observed.

ELIGIBLE PATIENTS with >1 NSCLC line (N=xxx)		
Acquired EGFR mutations at second-line treatment start	Del19	xxx (xx.x%)
	L858R	xxx (xx.x%)

ELIGIBLE PATIENTS with >1 NSCLC line (N=xxx)		
Other new genes alterations at start of second-line treatment?	Yes	xxx (xx.x%)
	No	xxx (xx.x%)
	UNK	xxx (xx.x%)
Other known genes alterations	ALK	xxx (xx.x%)
	HER2	xxx (xx.x%)
	KRAS	xxx (xx.x%)
	MET amplification	xxx (xx.x%)
	PI3KCA	xxx (xx.x%)
	PTEN	xxx (xx.x%)
	ROS1	xxx (xx.x%)
	Other gene(s) mutated (*)	xxx (xx.x%)

(*) listing might be provided depending on the number of cases observed.

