	L858R	xxx (xx.x%)
	L858X (with X being unequal to R)	xxx (xx.x%)
	T790M de novo	xxx (xx.x%)
	G719X	xxx (xx.x%)
	L861Q	xxx (xx.x%)
	S768I	xxx (xx.x%)
	E709X	xxx (xx.x%)
	L747P/S	xxx (xx.x%)
	Q787Q	xxx (xx.x%)
	Exon 20 insertion (*)	xxx (xx.x%)
	Other EGFR mutation(s) (*)	xxx (xx.x%)
	Unknown EGFR mutational status	xxx (xx.x%)
Classification of EGFR uncommon mutations at second-line treatment stop/end of observation	T790M-positive	xxx (xx.x%)
	Exon 20 insertion-positive	xxx (xx.x%)
	Major uncommon mutations	xxx (xx.x%)
	Others	xxx (xx.x%)
	Compound mutations	xxx (xx.x%)

(*) listing might be provided depending on the number of cases observed.

ELIGIBLE PATIENTS with >1 NSCLC line (N=xxx)		
Acquired EGFR mutations at second-line treatment stop/end of observation	Del19	xxx (xx.x%)
	L858R	xxx (xx.x%)

ELIGIBLE PATIENTS with >1 NSCLC line (N=xxx)		
Other new genes alterations at second-line treatment stop/end of observation?	Yes	xxx (xx.x%)
	No	xxx (xx.x%)
	UNK	xxx (xx.x%)
Other known genes alterations	ALK	xxx (xx.x%)
	HER2	xxx (xx.x%)
	KRAS	xxx (xx.x%)
	MET amplification	xxx (xx.x%)
	PI3KCA	xxx (xx.x%)
	PTEN	xxx (xx.x%)
	ROS1	xxx (xx.x%)
	Other gene(s) mutated (*)	xxx (xx.x%)

(*) listing might be provided depending on the number of cases observed.

Table 16-UNC. Approaches for detection of mutations at second-line treatment stop/end of observation (ELIGIBLE PATIENTS of the Uncommon Mutation Cohort) – Secondary objective #3

		ELIGIBLE PATIENTS with >1 NSCLC line with re-evaluated mutational status (N=xxx)
Biologic sample(s) used for mutation testing	Tissue, Histological sample (solid biopsy)	xxx (xx.x%)
	Cytological sample	xxx (xx.x%)
	Blood (liquid biopsy)	xxx (xx.x%)
	Other (*)	xxx (xx.x%)
	UNK	xxx (xx.x%)
Methodology used for mutation testing	Amplification Refractory Mutation System (ARMS)	xxx (xx.x%)
	- ADx	xxx (xx.x%)
	- Qiagen	xxx (xx.x%)
	- Roche	xxx (xx.x%)
	- Super ARMS	xxx (xx.x%)
	- Other (*)	xxx (xx.x%)
	- UNK	xxx (xx.x%)
	ddPCR	xxx (xx.x%)
	BEAMing	xxx (xx.x%)
	Sequencing	xxx (xx.x%)
	- Sanger sequencing	xxx (xx.x%)
	- Pyrosequencing	xxx (xx.x%)
	- Other (*)	xxx (xx.x%)
	- UNK	xxx (xx.x%)
	Next-Generation Sequencing (NGS)	xxx (xx.x%)
	- Targeted NGS	xxx (xx.x%)
	- Whole-exome sequencing	xxx (xx.x%)
	- Whole-genome sequencing	xxx (xx.x%)
	- Other (*)	xxx (xx.x%)
	- UNK	xxx (xx.x%)
	Other	xxx (xx.x%)
	UNK	xxx (xx.x%)

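### Table 12-UNC (and 11-SEQ by reference) is specified as new non-EGFR gene alterations, but its footnote carries first-line alterations into the gene rows; the same rule leaves Table 15-UNC/13-SEQ ambiguous

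*SAP*

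**What the plan says.** Table 12-UNC, in SAP 4.1.3, is to give the frequency of patients by "presence/absence of other new mutated genes and detail of new mutations at second-line treatment start". A footnote to the Yes/No field (MUT2_oth_gene_start_YN) adds that when the answer is 'No', the patient's "mutational status for other genes at second-line treatment start will be imputed as the same" as the status at first line. The layout in SAP 5.1.3 has two items: a Yes/No row, "Other new genes alterations at start of second-line treatment", and a list of genes (ALK, HER2, KRAS, MET amplification, PI3KCA, PTEN, ROS1, other) headed "Other known genes alterations".

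Table 15-UNC repeats the rule one step later. For a 'No', "mutational status for other genes at second-line treatment stop/end of observation will be imputed as the same" as at second-line start. Here the Section 4 text reads "presence/absence of other mutated genes and detail of mutations at second-line treatment stop/end of observation", without the word 'new', but the layout's Yes/No row reads "Other new genes alterations at second-line treatment stop/end of observation".

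Tables 11-SEQ and 13-SEQ refer to the corresponding uncommon-cohort tables and do not change the rule (SAP 4.2.3 and 5.2.3).

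For patients given afatinib and then osimertinib, protocol 9.7 states that "the proportion of patients with different types of resistance mutations observed at the time of discontinuation of osimertinib will be categorized and tabulated".

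**The concern.** A rule that fills a 'No' with the earlier status suits a variable describing current status. It does not suit a variable describing what is new, where 'No' should contribute nothing. In Table 12-UNC the SAP attaches the status rule to content that it describes as new.

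What is at stake is the interpretation of co-alterations such as MET, HER2, KRAS or PI3KCA. In the sequencing cohort, Table 13-SEQ is the only visible SAP table of mutations at osimertinib stop. If it is used for the protocol's resistance summary, an alteration present before osimertinib could be taken for one that emerged on it.

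**Working it through.** The plan states no figure for this point, so there is none to reproduce. The check is a trace of the rule followed by an illustration of size.

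**One patient.** Take KRAS present at first line and 'No' at second-line start. In Table 12-UNC the patient counts as 'No' in the Yes/No row and adds one to the KRAS row, which Section 4 calls detail of new mutations. If the answer at stop is again 'No', the same KRAS is carried into Table 15-UNC (13-SEQ for a sequencing-cohort patient).

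**Three readings of the gene rows.**

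1. They show new alterations, as the Table 12-UNC text says. The footnote then overcounts every 'No' patient with an earlier alteration.
2. They show current status, and the detail field for 'Yes' patients holds only new genes. Earlier genes of 'Yes' patients are then lost. A patient with KRAS at first line and new MET at second-line start appears under MET only. A later 'No' at stop copies that incomplete record.
3. They show current status, and the detail field holds the full list. The rows are then coherent, but the Table 12-UNC text describing them as new is wrong.

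Under each reading something in the SAP needs changing. The documents do not show the eCRF label or say what the detail field holds, so they do not settle which reading applies.

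**Size.** For one gene, let b be its prevalence at the earlier time point, g the share newly altered in that gene, and y the share answering 'Yes', so P('No') = 1 − y. All three are assumptions. Assume also that the answer is independent of b and that the 'Yes' detail field holds only new genes. Per 100 re-tested patients:

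- gene row as specified = 100 × [g + (1 − y) × b]
- true new = 100 × g
- full current status = 100 × (g + b)
- excess over new = 100 × (1 − y) × b

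| b | P('No') | g | Row as specified | True new | Excess | Ratio |
|---|---|---|---|---|---|---|
| 2% | 70% | 10% | 10 + 0.70 × 2 = 11.4 | 10.0 | 1.4 | 1.14 |
| 5% | 90% | 5% | 5 + 0.90 × 5 = 9.5 | 5.0 | 4.5 | 1.90 |
| 20% | 95% | 2% | 2 + 0.95 × 20 = 21.0 | 2.0 | 19.0 | 10.5 |

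The first and last rows are the extremes of the range examined. In the middle row, full status would be 5 + 5 = 10.0, so the specified row (9.5) equals neither quantity. The shortfall of 0.5 is y × b = 10% × 5%, the earlier alterations of 'Yes' patients.

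If the detail field instead holds the full list, the footnote's own contribution is still (1 − y) × b, and the field adds y × b. The row then equals full status and exceeds the new count by b.

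**Contrast with EGFR.** SAP chapter 3 defines EGFR status and acquired EGFR mutations as separate variables and obtains the second by comparing time points. No such pair is visible for the other genes.

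**The case against.** The strongest reply is that the gene rows were always meant as current status. Both layouts head them "Other known genes alterations", and Table 9-UNC uses the same heading at first line, where nothing can be new. The footnote itself speaks of status. The rule also parallels the EGFR status rule, where 'No' carries forward and 'Yes' reads the later field. On that reading a 'No' patient with earlier KRAS is correctly 'No' for new and correctly shown under a known alteration. Much of this stands: the Yes/No row is right, so the number of patients with any new alteration is not inflated. It does not remove the conflict with the Table 12-UNC text, which defines the rows as detail of new mutations.

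A reader might go further and infer that old alterations are reported as new throughout, including in the protocol's osimertinib resistance table. The documents do not support that. The Section 4 text for Table 15-UNC, which Table 13-SEQ takes over, omits 'new'; only the layout's Yes/No row has it. The SAP never calls Table 13-SEQ the resistance table. A dedicated one cannot be excluded, because SAP 4.2.7 has a heading with no visible content and the revision history names a Table 27-SEQ, beyond the last visible sequencing table (22-SEQ). Protocol 9.7 also speaks of mutations observed at discontinuation, not of newly acquired ones.

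Nor can one state as fact that the share of new alterations is nearly doubled, or that 'Yes' patients lose their earlier genes. The first depends on assumed rates and the second on a field that is not shown.

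**Conclusion.** The point holds for Table 12-UNC and, by reference, Table 11-SEQ. Section 4 text and footnote contradict each other, and following both puts pre-existing non-EGFR alterations into rows specified as new. For Table 15-UNC and Table 13-SEQ the finding is an ambiguity between text and layout. It becomes a risk of misreading if Table 13-SEQ is used to describe what emerged on osimertinib.

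The size is baseline prevalence times P('No'), about 1.4 to 19 per 100 re-tested patients over the assumed range. That 'No' means no new alteration is inferred from the table text and layout. The Table 12-UNC denominator is wider (all eligible patients with more than one line), so its percentages would be lower if some were not re-tested.

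The effect is confined to non-EGFR gene rows in descriptive tables. Acquired EGFR mutations, time on treatment, response and survival are unaffected.

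**What to change.** Replace the footnotes with two derived variables in SAP chapter 3, following the EGFR pattern.

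1. *New other-gene alterations.* 'No' means none, with no imputation. 'Yes' means the recorded genes that were not present at the earlier time point. This works whether the detail field holds new genes only or the full list.
2. *Other-gene status at that time.* For 'No', carry the earlier status forward. For 'Yes', take the union of the earlier and the recorded genes. Restrict to re-tested patients.

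Align the Section 4 text and Section 5 headings of Tables 12-UNC, 15-UNC, 11-SEQ and 13-SEQ so that each block states which variable it shows. For any statement about non-EGFR alterations emerging on osimertinib, use the first variable in re-tested patients who discontinued osimertinib. Table 13-SEQ also covers patients still on treatment at end of observation, whereas protocol 9.7 refers to discontinuation.

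The cost is a change of SAP wording and a few lines of code, using fields already collected.
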